6.2 REPORTING PROCEDURES

All adverse events will be reported. Depending on the nature of the event the reporting procedures below will be followed. Any questions concerning adverse event reporting should be directed to the Chief Investigator in the first instance.

6.2.1 Non serious AEs

All such events, whether expected or not, will be recorded.

6.2.2 Serious AEs

An SAE form will be completed and faxed to the Chief Investigator within 24 hours. However, relapse and death due to asthma and hospitalisations for elective treatment of a pre-existing condition do not need reporting as SAEs.

All SAEs should be reported to [name] where in the opinion of the Chief Investigator, the event was:

- ‘related’, ie resulted from the administration of any of the research procedures; and
- ‘unexpected’, ie an event that is not listed in the protocol as an expected occurrence

Reports of related and unexpected SAEs will be submitted within 15 days of the Chief Investigator becoming aware of the event, using the NRES SAE form for non-IMP studies. The Chief Investigator will also notify the Sponsor of all SAEs.

Any SAEs will be reported as required by the Local Research Ethics Committee, Sponsor and/or Research & Development Office.

There are no known SAEs from the use of these devices

It is not anticipated that there will be any SAE's with the use of the devices, however, should anything occur as a result of the device then the child will be followed up daily in the first instance then weekly for the next four weeks.

A period of four weeks of follow up care will occur after the last treatment for any adverse events to be recorded and reported.

Contact details for reporting SAEs

Fax: xxx, attention xxx

Please send SAE forms to: [name], Pharmacy Department, Royal Brompton Hospital.

[contact] [name] (Mon to Fri 09.00 – 17.00)

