6. ADVERSE EVENTS

6.1 DEFINITIONS

Adverse Event (AE): any untoward medical occurrence in a patient or clinical study subject.

Serious Adverse Event (SAE): any untoward and unexpected medical occurrence or effect that:

- **Results in death**

- **Is life-threatening** – refers to an event in which the subject was at risk of death at the time of the event; it does not refer to an event which hypothetically might have caused death if it were more severe
- **Requires hospitalisation, or prolongation of existing inpatients' hospitalisation**
- **Results in persistent or significant disability or incapacity**
- **Is a congenital anomaly or birth defect**

Medical judgement will be exercised in deciding whether an AE is serious in other situations. Important AEs that are not immediately life-threatening or do not result in death or hospitalisation but may jeopardise the subject or may require intervention to prevent one of the other outcomes listed in the definition above, should also be considered serious.

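### Section 6.2.2 lets asthma deaths and relapses leave the SAE route before anyone must judge and record whether a device contributed

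*Combined protocol and SAP*

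**What the plan says.** Section 6.1 of the protocol lists what makes an event serious. The list includes "Results in death" and "Requires hospitalisation, or prolongation of existing" inpatient stay, and no item excepts asthma.

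Section 6.2 opens with a general promise, "All adverse events will be reported", and then splits the route: "Depending on the nature of the event the reporting procedures below will be followed". Two procedures follow.

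- Section 6.2.1 is headed for non-serious events and says "All such events, whether expected or not, will be recorded".
- Section 6.2.2 requires an SAE form to reach the Chief Investigator within 24 hours, and then makes an exception: "However, relapse and death due to asthma and hospitalisations for elective treatment of a pre-existing condition do not need reporting as SAEs".

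After the exception, 6.2.2 sets the test for onward reporting within 15 days. In the Chief Investigator's opinion the SAE must be unexpected and must also be related, meaning that it "resulted from the administration of any of the research procedures". The same section adds: "The Chief Investigator will also notify the Sponsor of all SAEs".

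The Study Summary makes the devices' effect on asthma control one of the aims. Section 1.1 links poor adherence to exacerbations, admissions and asthma deaths.

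**The concern.** Exempting expected events of the underlying disease from SAE reporting can be legitimate. It is less comfortable here because the exempted events are of the kind through which a device problem could show itself. The participants are children from a difficult asthma clinic, and the devices either attach to the child's usual inhaler or work through a phone app. If a device or study procedure contributed to a serious event, that event could well look like asthma.

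The safeguard one would want is a recorded judgement on relatedness before the event leaves the SAE route. As written, the exemption comes first, and both the relatedness opinion and the notice to the Sponsor attach to what remains. At stake is the safety oversight of this study, and also the safety record available to the expert panel that will choose a device for a larger randomised trial. The usability and acceptability results are not at stake.

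**Working it through.** The plan has no figure to reproduce here, so the check is to follow each kind of event through the written procedures.

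| Event | 6.1 criterion met? | Covered by 6.2.1? | 6.2.2 as written | Relatedness opinion and Sponsor notice assured? |
|---|---|---|---|---|
| Death put down to asthma | Yes (death) | No, it is serious | Exempt | No |
| Life-threatening relapse without admission | Yes (life-threatening) | No, it is serious | Exempt | No |
| Emergency asthma admission | Yes (hospitalisation) | No, it is serious | Reportable, unless relapse is read to include it | Depends on the reading |
| Elective admission, pre-existing condition | Yes (hospitalisation) | No | Exempt by name | No, and not disputed |
| Any other serious event | Yes | No | SAE form within 24 hours | Yes |

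Three steps follow from the table.

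1. *Order of the tests.* The Chief Investigator's opinion on relatedness is stated for SAEs, to decide onward reporting. It is not a condition of the exemption. An event can therefore be exempted before that opinion is called for.

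2. *Where an exempted event goes.* Section 6.2 promises that every adverse event is reported, but through the procedures that follow it. One of these is for non-serious events and the other is the SAE route. The first two rows of the table fall between them.

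3. *Whether another clause closes the gap.* Section 6.2.2 sets a follow-up schedule for a child if something happens because of the device, but it does not say how that is established for an asthma event. The clause on ethics committee, Sponsor and R&D requirements is worded for SAEs and rests on rules outside the document. The four-week follow-up supports capture of adverse events but adds no relatedness step.

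A wording point bears on step 1: the lead-in to the SAE definition in 6.1 also requires the event to be unexpected. The argument does not rely on this, but it could be used to exclude a foreseeable asthma event from the definition altogether.

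*Scale.* The planned exposure is at most 30 × 16/52 = 9.2 child-years, or 30 × (16 + 4)/52 = 11.5 with the four-week follow-up. The documents give no rate of serious asthma events. Purely to size the paperwork, assume 0.05 to 0.5 per child-year from any cause. The expected count then runs from 9.23 × 0.05 = 0.5 to 11.54 × 0.5 = 5.8. The rates are assumptions without an anchor in the plan, and the counts include emergency admissions that may already need a form. They say nothing about how many events a device might cause.

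**The case against.** The case for leaving the text alone has several parts.

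- *The exemption already involves cause.* It covers events due to asthma, so someone must attribute them, and an event attributed to the device would fall outside it. This stands. What is missing is a requirement to consider the device and to record the answer.
- *A decision-maker is identifiable.* Section 6.2 sends reporting questions to the Chief Investigator first, and 6.2.2 makes that person's opinion the relatedness test. This also stands, but the first is a route for queries and the second applies to SAEs. Neither obliges anyone to refer an exempted event.
- *Emergency admissions probably stay reportable.* Only elective admissions are named as exempt, which suggests that emergency ones are not. This is the more natural reading, so the undefined term is a minor point.
- *Events are unlikely to be missed.* The general reporting promise, the telephone calls at day 7-14 and week 6-7, the week 4 download and the four-week follow-up all make capture likely. They do not supply a relatedness opinion or Sponsor notice.
- *No sign of harm.* Section 6.2.2 says that no SAEs are known from these devices, and Section 1.1 reports better adherence with existing monitors (30% versus 85%, and 49% versus 70%). A device contribution is possible but has no support in the documents. This limits the severity; it does not remove the gap.

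A reader might go further and infer that 6.1 and 6.2.2 flatly contradict each other, or that asthma deaths will go unrecorded. The documents support neither. Section 6.2.2 states an express exception to the SAE route, it permits omission from that route without forbidding a report, and the general promise on adverse events still applies.

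**Conclusion.** The point holds as a gap in safety reporting. Followed as written, an asthma death or serious relapse can leave the SAE route without a recorded judgement on device or procedure relatedness and without assured notice to the Sponsor, and neither written procedure clearly receives it. This rests on the text of 6.1 to 6.2.2 alone and needs no assumption about rates.

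The size is modest. The study plans for 30 children over up to 16 weeks, the number of affected events is unknown, and the primary outcome is untouched. It would be tempting to attach a probability that a device-related event is missed. That would need both an event rate and a device-related share, and the documents give neither, so no such figure should support the severity. Nor do the documents support a claim that the devices cause harm.

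**What to change.** Reconcile 6.1, 6.2, 6.2.1 and 6.2.2 as follows.

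1. Every death, and every asthma event that meets one of the seriousness criteria listed in 6.1, goes to the Chief Investigator on the existing SAE form within the existing 24 hours.
2. The Chief Investigator records a relatedness judgement covering both the device and the study procedures.
3. The asthma exemption then applies only to onward reporting of non-fatal asthma events judged unrelated.
4. The exemption for elective admissions stays.
5. As a minor clarification, state whether relapse covers an emergency asthma admission.

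Sending all serious asthma events, and not only those that may be related, matters: otherwise the first judgement on a non-fatal event would again be unassigned and unrecorded. For the same reason, item 1 should refer to the listed criteria, so that the word unexpected in the 6.1 lead-in cannot reopen the gap.

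The cost is a wording amendment and a few extra forms. The form, the recipient and the time limit already exist. The number of forms cannot be stated from the documents. At the assumed rates above, 0.5 to 5.8 serious asthma events would be expected in all, and fewer of these would be additional forms if emergency admissions are already reported.

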7. STATISTICS AND DATA ANALYSIS

Sample Size

This is largely a qualitative study, focusing on the views of the participants on the usability and acceptability aspect of the devices, though there is a component of quantitative analyses in the perceived accuracy of the device.

Qualitative studies are different from quantitative studies in that they attempt to identify themes rather than quantify results. Therefore power analyses to calculate sample size are difficult to conduct and based largely on thematic saturation (where no further themes can be found).

It has been argued that the main goal is to ensure that the sample size is small enough to manage the material and large enough to provide new and rich data (15).

Braun and Clark, 2013 offer a guide on sample size based on the size of the project (small, medium, large). They suggest that for small projects, 6-10 participants for individual

interviews, 2-4 for focus groups, 10-50 participants for individual interviews in medium projects and up to 100 or over for larger projects.

Fugard and Potts, 2015 (16), offer a tool to quantify sample sizes for thematic analyses in qualitative studies to help support choices and decision making. They feel that the concept of theoretical saturation, whereby collecting more data does not add further themes is problematic for prospective study planning. They recommend that for adjusted prevalence of 10%, 2 instances and 80%, 29 participants would be required.

Though our sample size of 30 participants, randomised into blocks of 10 per each platform roughly fits into this model, it is nonetheless subjective, as this is largely an exploratory study.

Data management

The data entry will be collected by the study investigator ([name]). The data analysis will be conducted by the study investigator ([name]) and the chief Investigator ([name]).

Additionally, an independent researcher will aid with the analysis of the themes for the qualitative aspect of the study to ensure there is no bias.

All data will be entered on a paper clinical report form (CRF) and all data entered on a database (Excel or Access) held on the secure RBH server.

Data analysis.

➤ Qualitative data

The focus group interviews will be audio recorded, transcribed and put into themes to conduct an inductive thematic analysis.

25% of the transcripts will be double coded by an independent researcher from UCL, [name], experienced in qualitative research.

The focus group interviews will be used to assess the usability and acceptability of the devices

➤ Quantitative data

The amount of usable data from each device will be quantified and compared.

This will provide data on the perceived accuracy of the device.

Additionally, data on asthma control and quality of life will be assessed.

These will be analysed quantitatively statically using the Statistical Package for the Social Services (SPSS). Data will be tested for normality using visual inspection, histograms and Kolmogorov-Smirnov testing. Parametric tests will be used if the data is normally distributed. If the data is not normally distributed or there are only small numbers non parametric tests will be used or the data will be logarithmically transformed. The significance levels for all tests will be set at <0.5.

Comparative analysis of variance between 2 groups for continuous data will be performed using the student's t test for normally distributed data and the Mann Whitney U tests for non normally distributed data and for more than 2 groups the ANOVA or Kruskal Wallis respectively. A comparison of the proportions between groups will be performed using the Pearson Chi 2 tests.

The quantitative and qualitative results will be amalgamated and an evidence report prepared to assess the feasibility of each device.

An expert panel will be convened to select the most appropriate device to take forward to a larger randomised controlled trial to assess the impact of the device on adherence in children with asthma.

Data and all appropriate documentation will be stored for a minimum of 10 years after the completion of the study, including the follow-up period.

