APPENDIX 1. SUMMARY OF INVESTIGATIONS, TREATMENT AND ASSESSMENTS		
	24	

GLOSSARY OF ABBREVIATIONS

KEYWORDS

Electronic monitoring device (EMD)
Novel electronic monitoring device (NEMD)
Compliance
Adherence
Children
Asthma

STUDY SUMMARY

TITLE	A feasibility study to assess novel electronic monitoring devices for monitoring adherence in children with asthma
DESIGN	A mixed method (quantitative and qualitative) open label, block randomised feasibility study
AIMS	
 1. To assess the feasibility of 4 novel electronic monitoring devices in children aged 6-16 years with asthma, in terms of usability and acceptability by patients/ guardians and healthcare professionals (qualitative study) 2. To evaluate the accuracy of these devices and assess whether they impact on asthma control (quantitative study)
OUTCOME MEASURES	
Primary outcome: Acceptability and usability of devices to participants and healthcare professional at Royal Brompton and Harefield NHS foundation Trust (RBHT)
 
Secondary outcomes:
 
 1. Accuracy of the adherence data collected from the devices. 2. Effect on asthma control as measured by asthma control test (ACT) or childhood asthma control test (cACT) score; exhaled nitric oxide (FENO), spirometry (FEV1) and bronchodilator reversibility (BDR).
POPULATION	Children aged 6-16 years with asthma on inhaled corticosteroid therapy.
ELIGIBILITY	Children aged 6-16 years with a diagnosis of asthma on inhaled corticosteroids who are being treated or followed up by the paediatric respiratory difficult asthma clinic at Royal Brompton hospital.
DURATION	Up to 16 weeks

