2. STUDY OBJECTIVES

Research question: Which novel electronic monitoring device (NEMD) (measuring both inhalation & activation) is the most feasible to use as a tool for monitoring adherence in children aged 6-16 years with asthma in terms of accuracy, usability and acceptability?

Aim: To conduct a feasibility study looking at four new electronic monitoring devices to monitor adherence in children with asthma aged 6-16 years prescribed inhaled corticosteroids.

Our primary objective is to assess which novel electronic monitoring device is the most feasible to use as a tool for monitoring adherence in children with asthma, in terms of its perceived accuracy, usability and acceptability by patients/guardians and healthcare professionals by using a face to face focus group discussion meeting or one to one interviews.

For the purposes of this study feasibility is the overarching term used to assess if the devices are capable of being used in clinical practice to monitor adherence.

Accuracy of the device will be assessed by capturing usable data from the devices. Usability of the device will be assessed from the focus group or one to one interviews encompassing ease of use, time taken, problems encountered, easy to learn to use the device.

Acceptability will also be assessed from the focus group discussions or one to one interviews in terms of aesthetically pleasing, liked the device, fits in with day to day living.

Our secondary objective is to evaluate the effect on asthma control as measured by asthma control test (ACT) or childhood asthma control test (CACT) score; exhaled nitric oxide (FENO), spirometry (FEV1) and bronchodilator reversibility (BDR)

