3. STUDY DESIGN

This is an open label, block randomised (10 in each block), mixed method (quantitative and qualitative) study to be conducted for a period of up to 16 weeks

Children aged between 6-16 years with asthma attending the paediatric respiratory difficult asthma clinic will be recruited into the study and randomly allocated to one of three arms using block randomisation matched for age and size of group. Children will be assigned to trial one of the following four NEMD's to be tested:

1. Block 1 (10): Smartinhaler Plus™ (Adherium, New Zealand)
 - This measures inhalation usually flow sensors and is the next generation of a currently commercially available EMD
2. Block 2a (5) : Flo-Tone (Clement Clarke, UK) plus Rafi-tone, acoustic enabled Smartphone App (clin-e-cal, UK) for children aged 6 – 11 years
 - The Flo-Tone attaches to an MDI and makes a sound when the inhaler is used correctly. Rafi-tone is a Smartphone App that detects the sound and activates a game. The game is aimed at younger children and therefore children aged 6 – 11 years will be randomised to this block.
- Block 2b (5) : Inhaler Compliance Assessment (INCA™) device (INCA, Ireland)
 - This is an audio recording device which attaches to a Diskus dry powder inhaler. Analysis of the digital audio recordings enables objective assessment of inhaler use and technique. As it can only be used with a Diskus only children ≥ 12 years will be randomised to this block
3. Block 3: Video and Remote Directly Observed treatment (rDOT)
 - Children are filmed on a Smartphone using their inhaler. The clip is then automatically uploaded via a Smartphone App (Continga, UK) and reviewed by a Clinical Nurse Specialist to ensure inhaler technique is correct.

Recruitment

30 children will be recruited into the study; 10 per block (5 per block aged 6-11 years and 5 aged 12-16 years)

Visit 1: Novel electronic monitoring device (NEMD) issued

Routine clinical care assessments will be carried out at the end of the study period as below, including asthma control test (ACT) or the childhood asthma control test (cACT), exhaled nitric oxide (FeNO) and spirometry (FEV1 and BDR) .

Patient/parent/Carer will be invited to take part in the study.

Information regarding the study and its objectives will be communicated to the Patient/parent/carer in both oral and written form using patient information leaflets.

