Where possible a second researcher from University College London (UCL), [name] will sit in the focus groups discussion and interviews to ensure there is no bias.

The conversations from the focus group and one to one interviews will be transcribed and coded into themes. We will utilise an external company for transcribing the conversations called 1st Class. <https://www.1stclass.uk.com/>

Analysis

Qualitative:

The focus group and one to one interviews will be audio recorded, transcribed and put into themes to conduct an inductive thematic analysis. 25% of the transcripts (8) will be double coded by an independent researcher from UCL, [name], experienced in qualitative research to ensure that the correct themes have been used and to ensure that there is no bias.

The focus group and one to one interviews will be used to assess the usability and acceptability of the devices

Quantitative:

[figure not shown]
The amount of usable data from each device will be quantified and compared.

This will provide data on the perceived accuracy of the device.

The quantitative and qualitative results will be amalgamated and an evidence report prepared to assess the feasibility of each device.

An expert panel will be convened to select the most appropriate device to take forward to a larger randomised controlled trial to assess the impact of the device on adherence in children with asthma.

REFERENCE DIAGRAM

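### The sample-size paragraph's 10 per platform does not match the 10/5/5/10 allocation by device, and device comparisons for the panel state no age band although two devices each cover only one

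*Combined protocol and SAP*

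**What the plan says.** The Sample size part of section 7 closes its argument with "Though our sample size of 30 participants, randomised into blocks of 10 per each platform roughly fits into this model".

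Section 3 describes the allocation differently. Children are "randomly allocated to one of three arms using block randomisation matched for age and size of group", yet four devices are to be tried. Block 1 is Smartinhaler Plus, marked 10. Block 2 is split into 2a, Flo-Tone with Rafi-tone, marked 5, and 2b, INCA, marked 5. Block 3 is rDOT and has no number beside it. The Recruitment paragraph adds "30 children will be recruited into the study; 10 per block (5 per block aged 6-11 years and 5 aged 12-16 years".

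The two halves of Block 2 are separated by age. For Flo-Tone: "The game is aimed at younger children and therefore children aged 6 – 11 years will be randomised to this block". For INCA: "As it can only be used with a Diskus only children ≥ 12 years will be randomised to this block".

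The questions and outputs are at device level. The research question in section 2 asks which device "is the most feasible to use as a tool for monitoring adherence in children aged 6-16 years with asthma". The study summary gives "Primary outcome: Acceptability and usability of devices to participants and healthcare professional", and the Analysis part of section 3 says "The focus group and one to one interviews will be used to assess the usability and acceptability of the devices". Sections 3 and 7 both say that the amount of usable data will be compared by device, that a report will assess the feasibility of each device, and that an expert panel will then select one for a larger randomised trial. Neither section states an age band for any of this. Section 7 names tests for two groups and for more than two, without saying whether a group is a block or a device.

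**The concern.** The first problem is a count. Section 1.2 uses the word platforms for the monitoring systems themselves, so a reader of section 7 will take it that each device is tried by 10 children. Two of the four devices have half that number.

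The second follows from how Block 2 was built. Age was balanced at allocation, so whole blocks are comparable on age. The panel does not choose a block, however; it chooses a device. Once Block 2 is split into its two devices, each holds a single age band, while Smartinhaler Plus and rDOT hold both. A device comparison that ignores band then mixes the device with the age of the children who tried it. At stake is whether Flo-Tone or INCA looks better or worse to the panel partly because of who used it.

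**Working it through.** **The plan's own figure.** Section 7 cites 29 participants for a theme of 10% prevalence, at least 2 instances and 80% probability. The exact binomial is P(X ≥ 2) = 1 − 0.9^n − n × 0.1 × 0.9^(n−1). At n = 28 it is 0.785, at n = 29 it is 0.801, and at the planned n = 30 it is 0.816. The 29 reproduces, and 30 exceeds it.

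**Allocation by device and age band** (section 3, block list and Recruitment):

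| Device | 6-11 | 12-16 | Total |
|---|---|---|---|
| Smartinhaler Plus | 5 | 5 | 10 |
| Flo-Tone/Rafi-tone | 5 | 0 | 5 |
| INCA | 0 | 5 | 5 |
| rDOT (inferred from 10 per block) | 5 | 5 | 10 |
| All | 15 | 15 | 30 |

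By device: 10 + 5 + 5 + 10 = 30. Ten per device would need 4 × 10 = 40. Ten per block gives 3 × 10 = 30.

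**Age imbalance.** The documents give no age effect, so let G be an assumed difference in mean usable data between the bands, with no true device difference. If the 6-11 mean is m and the 12-16 mean is m + G, a 5 + 5 device averages m + G/2, Flo-Tone averages m and INCA averages m + G. The false differences are:

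- Flo-Tone or INCA v Smartinhaler Plus or rDOT: G/2 in size
- Flo-Tone v INCA: G
- whole block v whole block, or any two devices within one band: 0

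For assumed values of G of 10, 20 and 30 percentage points, the first is 5, 10 and 15 points and the second is 10, 20 and 30 points.

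**Precision.** For Flo-Tone or INCA against a mixed-age device, the 95% half-width in units of the within-band SD is t(0.975, df) × √variance:

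- unstratified, 5 v 10: variance 1/5 + 1/10 = 0.30, df 13, 2.160 × 0.548 = 1.18 SD
- within band, 5 v 5: variance 1/5 + 1/5 = 0.40, df 8, 2.306 × 0.632 = 1.46 SD
- device-plus-age-band model on all 30: the band effect is estimated from Smartinhaler Plus and rDOT, 10 v 10, with variance 0.20, and half of it is applied, so the variance is 0.30 + 0.20/4 = 0.35; df = 30 − 5 = 25, and 2.060 × 0.592 = 1.22 SD

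The model assumes no device-by-age interaction. Setting the unstratified mean squared error, 0.30 + G²/4, equal to 0.40 gives G = 2√0.10 = 0.63 SD; equal to 0.35 gives G = 2√0.05 = 0.45 SD. Handling age lowers the error of a single contrast only when the age gap exceeds these values, although both methods remove the imbalance whatever its size (the model, if additivity holds).

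**The case against.** The strongest reply is that little turns on this. The sentence in section 7 states a total of 30 in blocks of 10, which can only mean three blocks, and section 3 sets out the split openly. The study calls itself largely qualitative and exploratory. Nothing says that an unstratified four-device test will be run, and an expert panel that knows the devices can allow for age. A figure in the Quantitative part of section 3 is not available to us and might show more.

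Much of this stands. The count is a wording error that changes neither the total nor the benchmark. A reader might infer that the plan commits to an age-blind test of four devices; it does not, because section 7 leaves the groups undefined. The objection does not remove the gap. Disclosing the age limits in the design section is not a rule for the analysis, and the text of section 7, which parallels section 3, states no age band either.

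The objection also limits the remedy. The nurses' separate focus group has no child age band. Section 3 does not say that family focus groups are divided by device or age, so splitting every theme by band cannot be required.

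**Conclusion.** The point holds as a minor one. The per-platform figure in section 7 conflicts with section 3 for two of the four devices: 5 each, not 10. As written, device comparisons involving Flo-Tone or INCA are not protected against age. A direct difference between those two cannot be separated from age, and any INCA contrast also reflects the Diskus inhaler, which age bands cannot remove.

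This rests on three readings: that platform means device, as in section 1.2; that rDOT has 10, which is inferred rather than printed; and that no age band appears in the missing figure.

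Three stronger conclusions might be drawn, and the documents do not support them. One is that 30 is too few or should be 40: the benchmark is met by the total, and the plan nowhere requires 10 per device beyond the faulty phrase. Another is that the sample fails to detect themes for each device: the protocol makes no such claim. The third is that the panel's choice will be biased by a known amount: no age effect is given, so the values of G above are only illustrations.

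**What to change.** 1. In section 7, Sample size, replace the phrase about 10 per platform with: randomised in three blocks of 10 (Smartinhaler Plus 10; Flo-Tone/Rafi-tone 5, ages 6-11, and INCA 5, ages 12-16; rDOT 10).
2. In the analysis parts of sections 3 and 7, state that usable data by device will be shown to the panel within the allocation age bands, descriptively and with intervals: Smartinhaler Plus, Flo-Tone and rDOT at 6-11; Smartinhaler Plus, INCA and rDOT at 12-16; 5 children in each cell. Any overall four-device comparison will adjust for age band. A direct Flo-Tone v INCA difference will be reported as not separable from age, and INCA contrasts as also reflecting the Diskus.
3. Label child and parent feedback on usability and acceptability by device and age band where the interview or focus-group format allows. Report nurse feedback by device only.

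The cost is wording and one table, with no extra children. The cells are imprecise: the half-width for Flo-Tone or INCA against a mixed-age device rises from 1.18 SD to 1.46 SD within band, or to about 1.22 SD with the device-plus-age-band model if there is no device-by-age interaction. Banding does not settle how a device tried in one band could be chosen for the whole 6-16 range; that remains for the panel.

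### The 29-participant rule supports the sample of 30 only for themes common to all devices; for themes about one device it gives about 26% (10 children) or 8% (5 children), not 80%

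*Combined protocol and SAP*

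**What the plan says.** Section 7 (Sample Size) explains that power calculations are hard to apply to qualitative work and then cites two guides. One sizes a study by the scale of the project: "They suggest that for small projects, 6-10 participants for individual" interviews, with separate ranges for focus groups and for larger projects. The other is a quantitative tool: "They recommend that for adjusted prevalence of 10%, 2 instances and 80%, 29 participants would be required". The section concludes "Though our sample size of 30 participants, randomised into blocks of 10 per each platform roughly fits into this model", adding that the number is still subjective because the work is exploratory.

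Section 2 puts the question at device level: "Our primary objective is to assess which novel electronic monitoring device is the most feasible to use as a tool for monitoring adherence". Sections 3 and 7 then call for a report on the feasibility of each device and an expert panel that picks one for a larger randomised trial.

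Section 3 allocates each child to one device. There are three blocks of 10 children but four devices, because the second block is split by age: 5 children aged 6-11 on the Flo-Tone with its app (2a), and 5 aged 12 or over on the recorder ("Block 2b (5) : Inhaler Compliance Assessment"). The device groups are therefore 10, 5, 5 and 10.

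**The concern.** The rule of 29 treats every respondent as someone who could raise the theme. A remark about how easy a device is to use, or whether the child likes it, can come only from those who were given it. The sentence claiming the fit names the split by platform and the pooled total together, so a reader may take the 80% to apply to the comparison the study is meant to inform. It also describes every platform as having 10 children, which section 3 contradicts for devices 2a and 2b.

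At stake is how much weight the panel gives to what was not said about a device. The groups differ in size by a factor of two, so a problem of the same prevalence is less likely to be heard for the 5-child devices.

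**Working it through.** **Inputs.** From section 7: prevalence p = 0.10, at least 2 instances, probability 0.80, stated requirement 29, planned total 30. From section 3: 10 children in each of blocks 1 and 3, and 5 on each of devices 2a and 2b. Assumptions: independent respondents, and every child interviewed.

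**Formula.** With X ~ Binomial(n, p), P(X ≥ 2) = 1 − (1 − p)^n − n·p·(1 − p)^(n−1).

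**The plan's own figure.**
- n = 28: 1 − 0.0523 − 0.1628 = 0.785
- n = 29: 1 − 0.0471 − 0.1518 = 0.801

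The smallest n reaching 0.80 is 29, as stated. At n = 30 the probability is 0.816.

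**The same rule per device, children only.**
- n = 10: 1 − 0.3487 − 0.3874 = 0.264
- n = 5: 1 − 0.5905 − 0.3281 = 0.081

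**One carer per child, counted as a fully independent respondent (an upper bound).**
- 10 children, n = 20: 1 − 0.1216 − 0.2702 = 0.608
- 5 children, n = 10: 0.264

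**Chance that no child voices a 10% problem, P(X = 0) = 0.9^n.**
- n = 10: 0.349, or 35%
- n = 5: 0.590, or 59%

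**Prevalence at which P(X ≥ 2) = 0.80.**
- n = 10: p = 0.271
- n = 5: p = 0.490
- n = 29: p = 0.100

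**Sensitivity to prevalence, P(X ≥ 2).**

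| Prevalence | n = 5 | n = 10 | n = 30 |
|---|---|---|---|
| 10% | 0.081 | 0.264 | 0.816 |
| 20% | 0.263 | 0.624 | 0.989 |
| 30% | 0.472 | 0.851 | >0.999 |
| 50% | 0.813 | 0.989 | >0.999 |

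**The case against.** **The plan does not promise 80% per device.** It reports what a tool gives, calls the fit rough and the choice subjective, and warns that such calculations suit qualitative work poorly. This stands, and it lowers the severity. But a rough fit describes 30 against 29; it does not tell the reader that the figure is 26% or 8% at the level where the panel decides.

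**More people speak than the 30 children.** Section 3 includes carers in the interviews and adds a nurse focus group, and professionals' views belong to the primary outcome. This also stands: 26% and 8% count children only. Even the most generous treatment of carers stays below 80%. A carer and child sharing one device will often report the same experience, so the true gain is smaller. The number of nurses is not stated, so the rule cannot be applied to them.

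**Stronger readings that the documents do not support.**
- A reader might take 1 − 0.081 = 92% as the chance that a 10% problem goes unheard with 5 children. It is the chance of fewer than two mentions. Complete silence has probability 59%; in the remaining 33% one child raises it, and nothing in the plan discards a point raised once.
- A reader might infer that silence will count in a device's favour. The plan describes inductive thematic analysis and panel judgement, with no rule that scores themes.
- A reader might suppose that focus-group correlation makes every figure worse. With a beta-binomial model and illustrative intraclass correlations of 0.1, 0.2 and 0.5, the 5-child figure rises to 0.112, 0.126 and 0.130. Ten children in two groups of 5 stay at about 0.27 for correlations of 0.1 to 0.2.
- A reader might say that 5 falls below the smallest range section 7 quotes. The same sentence gives 2-4 for focus groups, and that guide concerns whole projects, not subgroups.
- A reader might add a loss rate. The documents give none, and the eight-week threshold in section 4.4 concerns adherence data, not interviews.

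**Conclusion.** The concern holds as a matter of scope. The arithmetic behind 29 is correct, but it supports the sample of 30 only for themes that users of any device could raise. For themes about one device, the plan's rule gives about 26% for the two devices with 10 children and 8% for the two with 5; with carers counted as fully independent, at most about 61% and 26%. Statements about 10 children per platform do not hold for devices 2a and 2b.

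These figures assume independent respondents, 10% prevalence and full interview participation. Illustrative clustering moves the per-device values only slightly, and a 20% prevalence still leaves both group sizes below 80%. Severity is moderate: the sample-size rationale omits something the panel should know, but neither the design nor the analysis is invalid, and the plan already hedges the claim.

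**What to change.** In section 7, replace the sentence claiming the fit with a statement covering three points:
- The total of 30 gives roughly 80% probability of two instances of a 10% theme only for themes common to all devices.
- For themes specific to one device, 80% probability of two instances needs a prevalence of about 27% with 10 children or about 49% with 5, assuming independent respondents.
- Two of the four devices (2a and 2b) have 5 users each, not 10.

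In the evidence report, print the number of respondents per device beside each theme, and state that absence of a theme for a device is not interpreted as absence of the problem.

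The cost is a few sentences and one report column. No children are added, and allocation and analysis stay as they are. (Keeping 80% per device at 10% prevalence would take 4 × 29 = 116 children, which is not proposed for a feasibility study.) The downside is that the stated sample-size figure becomes less favourable.
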